Cerebellar tDCS, gait and balance training in PwMS

PI: [name]
IRB ID #: 201912430

Project Details

I. Project Introduction

I.1 *Project to be reviewed by:*
IRB-01

I.2 *Project Title:*
The effects of 4 mA cerebellar transcranial direct current stimulation combined with gait and balance training in people with multiple sclerosis

I.3 *Short Title (optional):*
Cerebellar tDCS, gait and balance training in PwMS

I.4 *Provide a short summary of the purpose and procedures of the study proposed in this IRB application.*

- **DO NOT include information on studies not proposed in this application.**
- **Use LAY terminology only. This must be easily understandable by IRB community members and nonscientists.**
- **DO NOT cut and paste technical abstracts from funding applications that may not be understood by a general audience.**

The purpose of this study is to investigate the effects of cerebellar transcranial direct current stimulation (tDCS) combined with gait or balance training on glucose uptake in the leg muscles as well as gait and balance performance. We will conduct tDCS or SHAM followed by balance or gait training over 9 days. We will evaluate gait and balance with well-established functional tasks and changes in glucose uptake with PET-FDG imaging.

I.5 *Specify your research question(s), study aims or hypotheses (do not indicate "see protocol")*
Our research question is whether tDCS combined with gait and balance training can improve gait and balance performance as well as increase glucose uptake symmetry in the leg muscles of people with multiple sclerosis. We hypothesize that gait, balance, and glucose uptake symmetry will improve in both groups that received training (gait or balance) combined with tDCS compared to the groups that only receive training (sham tDCS). Moreover, we hypothesize that the greatest improvements will be seen in the gait and tDCS group.

I.6 *Background and significance and/or Preliminary studies related to this project. (do not indicate "see protocol")*

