V.26 *The study involves Department of Nursing Services and Patient Care nursing, nursing resources or evaluates nursing practices at UI Health Care.*
 No

VI. Subjects

VI.1 *How many adult subjects do you expect to consent or enroll for this project?*
 48

VI.2 *What is the age of the youngest adult subject?*
 18.0

VI.3 *What is the age of the oldest adult subject?*
 75.0

VI.4 *What is the percentage of adult male subjects?*
 30

VI.5 *What is the percentage of adult female subjects?*
 70

VI.6 *How many minor subjects do you expect to consent or enroll for this project?*
 0

VI.13 *Describe EACH of your subject populations*

- *Include description of any control group(s)*
- *Specify the Inclusion/Exclusion criteria for EACH group*

Inclusion criteria: medically diagnosed with relapsing-remitting multiple sclerosis, 18-75 years of age, moderate disability (score of 2-6 on the Patient Determined Disease Scale [PPDS]), self-reported differences in function between legs, able to walk on a treadmill for at least 20 mins, and not taking any psychoactive medication.

Exclusion criteria: relapse within the last 60 days, have changed disease modifying medications in the last 45 days, are currently pregnant, have a concurrent neurological or neuromuscular disease, have been hospitalized within the last 90

days, have any contraindications for the tDCS device (i.e., pacemakers or metal implants), or are unable to understand/sign the consent form.

VI.14 *Provide an estimate of the total number of subjects that would be eligible for inclusion in each of your study populations (include your control population if applicable)*
48

VI.15 *Describe how you will have access to each of your study populations in sufficient number to meet your recruitment goals.*
We will generate a list of MS patients from our population seen in the Neurology clinic whose diagnosis is listed as MS in Epic. Furthermore, we will distribute flyers around the UIowa clinics and hospital.

VI.16 *Do you plan to recruit/enroll non-English speaking people?*
No

VI.18 *Do you propose to enroll any of the following in this study as subjects?*

- *Employee of the PI or employee of a research team member*
- *Individual supervised by PI or supervised by member of research team*
- *Individual subordinate to the PI or subordinate to any member of the research team*
- *Student or trainee under the direction of the PI or under the direction of a member of the research team*

No

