VII.B.31 *Provide a detailed rationale for why this device meets the FDA definition of a Non-Significant Risk Device (NSR)*
Numerous studies used this device without any serious side effects. Additionally, the attachment "tDCS Safety" provides more details regarding the safety of tDCS.

VII.B.32 *Provide a summary of prior investigations with this device.*
The PI and [name] (Faculty Mentor) used this device in previous studies, published in the journal Brain Sciences.

Furthermore, the IRB has approved protocols 201905826, 201905825, and 201906759 that are using this same device under similar stimulation parameters.

[name], [name], [name] Transcranial Direct Current Stimulation at 4 mA Induces Greater Leg Muscle Fatigability in Women Compared to Men. Brain Sciences, doi: doi: 10.3390/brainsci10040244 (2020).

[name], [name], [name] Cerebellar Transcranial Direct Current Stimulation in People with Parkinson's Disease: A Pilot Study. Brain Sciences, doi: doi:

10.3390/brainsci10020096 (2020).

VII.B.33 *Have there been any prior IRB reviews (at UI or elsewhere) and/or determinations made with regard to this device?*

Yes

VII.B.34 *Provide a discussion of these reviews/determinations.*

The Faculty Mentor ([name]) used a tDCS device at Colorado State University. CSU IRB approved the protocols without any concerns. All protocols have been completed without any problems. Furthermore, our previous approved protocols (IRB #201905826, #201905825, #201906759, #202005124, #202002425, #201912430, and #202006616) included this same tDCS device.

VII.B.35 *Has the FDA made an assessment of risk with regard to this device?*

Yes

VII.B.36 *Has this device/software been approved by the FDA for another indication or in another form from its use in this project?*

No

VII.C. Project Description (C)

VII.C.1 *Does this project involve any research on genes or genetic testing/research?*

No

VII.D. Project Description (D)

VII.D.1 *Check all materials/methods that will be used in recruiting subjects (you will need to attach copies of all materials at the end of the application):*

- E-mail -
- Advertisements -

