- *Procedures include a confederate pretending to be another participant in the study.*
- *Participants will be told that the research includes completion of a particular task, when in fact, that task will not be administered.*
- *Study is designed to introduce a new procedure (or task) that participants are not initially told about.*
- *If yes, a waiver of informed consent must be requested under question IV.3.*

No

VII.E. Project Description (E)

VII.E.1 *Will subjects be randomized?*
 Yes

VII.E.1.a *Will any subjects be blinded to which study arm they have been assigned?*
 Yes

VII.E.1.b *Does the protocol permit telling subjects their treatment assignment at the end of the entire study?*
 Yes

VII.E.1.c *Describe the circumstances under which subjects will be told what study arm they have been assigned.*
 At the end of all sessions the participant will be informed about the study arm in which they were involved.

VII.E.2 *Describe randomization scheme/assignment including ratio such as 1:1, 2:1 etc.*
 The study will be a double-blind and sham-controlled. Forty participants will be randomly assigned into four groups (Sham and balance training, 4 mA tDCS and balance training, sham and gait training, and 4 mA and gait training). Participants will undergo 9 sessions of tDCS combined with either gait or balance training.

VII.E.3 *Will any questionnaires, surveys, or written assessments be used to obtain data directly from subjects in this study?*
 Yes

VII.E.4 *List all questionnaires, surveys, written assessments and ATTACH each one to the application. (NOTE: You are NOT prohibited from attaching copyrighted materials to this application)*
 Patient Determined Disease Steps (PDDS)
 Fatigue Severity Scale (FSS)

VII.E.5 *Does this project involve creating any audiotapes, videotapes, or photographs?*
 No

VII.E.6 *Provide a detailed description in sequential order of the study procedures following the consent process - DO NOT cut and paste from the Consent Document.*

Describe study populations separately if they will be participating in different procedures - include CONTROL population if applicable.

DESCRIBE:

- *What subjects will be asked to do/what happens in the study (in sequential order)*
- *The time period over which procedures will occur*
- *The time commitment for the subject for individual visits/procedures*

- **Long-term followup and how it occurs**

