PwMS will be randomly assigned to one of four groups: ctDCS and gait training, sham and gait training, ctDCS and balance training, or sham and balance training (n = 12 per group). Each subject will attend a total of 14 experimental sessions. Session 1 will be a familiarization session and will last approximately 45 minutes. The duration of the baseline (Session 2) and 24-hour post-intervention session (Session 12) will be approximately 3 hours. The ctDCS and gait training sessions (Sessions 3 – 11) will last approximately 1.5 hours. Finally, the two- and four-week post-intervention sessions (Sessions 13 and 14, respectively) will be approximately one hour. During the initial session, subjects will be consented and complete strength testing to objectively determine the more-affected leg. Additionally, during Session 1 subjects will become familiar with treadmill walking and determine a self-selected speed for subsequent testing sessions. During the baseline session (Session 2), subjects will 1) complete the Fatigue Severity Scale (FSS)63, 2) undergo a whole-body FDG/PET scan after 20 minutes of treadmill walking at their self-selected speed, 3) perform the Functional Gait Assessment (FGA), 4) Timed 25-Foot Walk Test (T25WT), 5) Berg Balance Scale (BBS), 6) static posturography, and 7) the 6-minute walk test (6MWT) while wearing inertial sensors. The following 9 days will include 20 minutes of either 4 mA or sham ctDCS, 10 minutes of rest to allow for peak stimulation effects, and then approximately 40 minutes of gait or balance training. Session 12 will consist of the same testing battery as Session 2. Long term effects (2- and 4-weeks post-intervention) will be assessed with the 1) FSS questionnaire, 2) FGA, 3) T25FW, 4) BBS, 5) static posturography, and 6) the 6MWT during Sessions 13 and 14.

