A stimulation (sham vs. 4 mA) by training (balance vs. gait) by time (24 hours, 2 weeks, and 4 weeks) ANCOVA with baseline measurements as covariates will be conducted on each outcome variable (e.g., distance walked on the 6MWT and FGA score) to compare the short- and long-term effects of gait and balance training combined with ctDCS. Levene's test and normality tests (QQ plots, Shapiro Wilk test, and histograms) will be used to test the statistical assumptions. Post-hoc testing (paired and unpaired t-tests) and effect sizes (Cohen's d) will be calculated to clarify significant main or interaction effects. Significance will be accepted at $p < 0.05$ and adjusted with a Bonferroni correction. Statistical analyses will be performed using SPSS 27 (IBM Corp, Armonk, NY, USA).

XI.2*Provide the rationale or power analysis to support the number of subjects proposed to complete this study.*

We used effect sizes (Cohen's $d = 2.08$ and 1.37 , respectively) from Pilloni et al. 202060 and Hebert et al. 201146 to calculate the required sample size. With a significance fixed at $p = 0.05$ and 80% power, we will require 40 total subjects ($n = 10$ in each group) to properly power the hypothesis test for a statistically significant change. Based on this calculation and the assumption of a standard drop out rate of approximately 20%, we propose to recruit 48 total subjects ($n = 12$ in each group).

XII. Future Research

XII.1 *Do you wish to keep any information about subjects involved with this research project so that members of the current research team may contact them in the future for your own research projects?*
Yes

XII.2 *Do you wish to keep any information about subjects involved with this research project so that other researchers may contact them for future research?*
Yes

XII.3 *List the data or information you will keep:*
Contact information and outcome of the phone questionnaire.

XII.4 *Does this project involve storing any data, tissues or specimens for future research?*
Yes – contribution for future use is mandatory for participation in the study

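### No balancing or adjustment for sex is stated for four small arms, although the team cites a sex-dependent response at 4 mA; stratifying by sex would be a cheap improvement

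*Combined protocol and SAP*

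**What the plan says.** - **Allocation.** VII.E.2, the item that asks for the scheme and ratio, answers "Forty participants will be randomly assigned into four groups". VII.E.6 says "PwMS will be randomly assigned to one of four groups", with 12 in each. Neither states a ratio, block, stratum or minimisation factor. VII.B.11 answers that no separate written protocol exists, so none is promised elsewhere.
- **Sex mix.** VI.4 ("What is the percentage of adult male subjects") is answered 30, and VI.5 ("What is the percentage of adult female subjects") is answered 70.
- **Prior work.** VII.B.32 says that the team "used this device in previous studies, published in the journal Brain Sciences". One listed title is "Transcranial Direct Current Stimulation at 4 mA Induces Greater Leg Muscle Fatigability in Women Compared to Men". Only the title is given.
- **Analysis.** XI.1 plans a stimulation by training by time model: "ANCOVA with baseline measurements as covariates will be conducted on each outcome variable". Sex is not a factor or covariate, and no analysis by sex is described.
- **Hypothesis.** I.5 expects both active groups to beat their sham counterparts, and adds: "we hypothesize that the greatest improvements will be seen in the gait and tDCS group".

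**The concern.** The team's own reference list suggests that women and men may respond differently to the intensity used here. With about 12 to 14 men spread over four arms, simple random assignment can easily leave the arms with different sex mixes. If the response to 4 mA does depend on sex, the average effect in each active arm depends on who happened to land in it. The comparison most exposed is the one between the two active arms, because a different sex mix could then look like a difference between gait and balance training. An arm with no men, or one, cannot be repaired after randomisation.

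**Working it through.** **1. The plan's own sample size.** Inputs from XI.2: d = 1.37 (the smaller of the two effects), alpha 0.05 (two-sided assumed), power 80%. A two-sample t-test needs 9.43 per arm, so 10 per arm and 40 in total, as stated. 40 × 1.2 = 48 matches the recruitment figure. The change proposed below does not alter these numbers.

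**2. Expected men.** 0.30 × 48 = 14.4, taken as 14. 0.30 × 40 = 12. Both totals are carried because VII.E.2 says forty and VII.E.6 and XI.2 imply 48.

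**3. Chance imbalance.** Equal arms of size n = N/4 are assumed; the plan states no ratio. The probability that the arms hold (a, b, c, d) men out of M is C(n,a)·C(n,b)·C(n,c)·C(n,d) / C(N,M). Summing over the relevant splits:

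| Event | N = 48, 14 men | N = 40, 12 men |
|---|---|---|
| Some arm has 0 or 1 man | 26% | 43% |
| Some arm has no men | 3% | 6% |
| Largest and smallest counts of men differ by 4 or more | 40% | 33% |
| A given pair of arms differs by at least 30 points in share of women | 12% (4 or more of 12) | 23% (3 or more of 10) |
| Pooled active and sham differ by 4 or more men | 34% | 30% |

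**4. Effect on gait + tDCS versus balance + tDCS.** Let h be the sex difference in response to stimulation, in SD units. The documents give no value, so 0.5 to 2.0 is assumed. Shift = h × gap in share of women. For a 30-point gap: 0.5 × 0.30 = 0.15 SD; 1.0 × 0.30 = 0.30 SD; 2.0 × 0.30 = 0.60 SD. The standard error of a 10 v 10 contrast is √(2/10) = 0.447 SD.

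**5. Effect on pooled active versus sham.** Under a sex difference in response, only the active arms' mix matters. At N = 48 a 4-man difference is 9 v 5, so the active arms have 9/24 = 37.5% men against 14/48 = 29.2% overall, a departure of 8.3 points. With h = 1, the shift is 0.083 SD. A 6-man difference (10 v 4; 11% of allocations) gives 41.7% − 29.2% = 12.5 points, or 0.125 SD. The standard error of 24 v 24 is √(2/24) = 0.289 SD.

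**6. Type I error and variance.** In 100,000 simulated trials at N = 40 with no stimulation effect and no stratification, the active-versus-sham t-test rejects in 5.0% for assumed sex differences in the outcome of 0, 0.5 and 1.0 SD. The cost is precision: the standard error of a 10 v 10 contrast is 0.460 SD (0.5 SD sex difference) or 0.494 SD (1.0 SD), against 0.446 SD under stratification.

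**7. Stratified but not adjusted.** With stratification by sex and a t-test that ignores it, the rejection rate falls to 4.4% (0.5 SD) and about 3% (1.0 SD). The test becomes conservative, so sex belongs in the model too.

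**The case against.** A reader might infer that sex imbalance could pass for a stimulation effect, or biases the trial. The documents do not support that. The cited title describes a different response by sex. If 4 mA does nothing in either sex, no sex mix can produce an active-versus-sham difference by that route. A sex difference in the outcome itself could shift the estimate in one realised trial: given a 30-point gap at N = 40, the false-positive rate would be 6.1% for a pair of arms and 7.4% pooled at an assumed 0.5 SD, or 8.9% and 13.4% at 1.0 SD. But the documents give no evidence of such a difference, the figures are before baseline adjustment, and over all randomisations the rate stays at 5%. The ANCOVA already removes much of any sex difference present before treatment. All of this stands.

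The premise is also thin. The title gives no size, population or electrode placement, and unlike the other listed title it does not mention the cerebellum. Muscle fatigability is not a listed outcome; the Fatigue Severity Scale is a questionnaire. Outcomes are measured at 24 hours, 2 weeks and 4 weeks, in sessions for which VII.E.6 describes no stimulation. Relevance to gait, balance and uptake symmetry is therefore assumed. One could add that fatigability might change the training achieved, since treadmill speed and slope follow perceived exertion. That applies only to the aerobic bouts of gait training, and a change in training caused by stimulation is part of the randomised effect, not confounding.

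What survives the objection: baseline adjustment does not deal with a sex difference in response, and the comparison between the two active arms remains exposed to it.

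**Conclusion.** The point holds as a cheap improvement of low severity, not as an error in the plan. The documents are silent on balancing or adjusting for sex; they do not rule it out. Uneven sex mixes across four small arms are likely by chance. The consequence is extra variance and an average active effect that depends on the sex mix. For pooled active versus sham the shift is small: 0.08 to 0.125 SD for imbalances of 4 to 6 men and an assumed 1 SD sex difference in response, against planning effects of 1.37 and 2.08. For gait plus tDCS versus balance plus tDCS it could matter more, up to 0.60 SD at the top of the assumed range. These sizes rest on equal arms, 30% men as forecast, and an assumed sex effect supported only by a title.

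**What to change.** In VII.E.2, state 1:1:1:1 randomisation in permuted blocks stratified by sex. In XI.1, add sex as a covariate to the ANCOVA. If the team prefers neither, it should say why.

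With 28 women and 12 men this puts 7 women and 3 men in every arm. With 34 women and 14 men, blocks of four give 3 or 4 men and 8 or 9 women per arm. Varying the block size makes the next assignment harder to guess, but loosens that guarantee slightly.

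Stratification evens out the sex mix; the covariate restores the correct error rate and does not estimate a sex-specific effect. Any active-versus-sham results by sex should therefore be descriptive only, since 3 or 4 men per arm, before dropout, cannot establish one.

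Cost: two randomisation lists instead of one, one model degree of freedom, and an incomplete final block on each list. Sex is known at enrolment and the sample size is unchanged. The totals of 40 and 48 randomised should be reconciled in the same edit, though that is a separate matter.

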STRENGTH TESTING: Strength testing will be performed in a sitting position on an isokinetic dynamometer (CSMi, Stoughton, MA, USA). The subject will be secured with Velcro bands to help isolate the knee joint and the range of motion will be set between 100° and 0° of flexion. Strength testing will begin with a 15-repetition warm up of the knee extensors and flexors at 60/s (concentric/concentric). After a 30 second rest, 3 sets of 1 maximal effort isometric contraction of the knee extensors and flexors will be performed at 65° and 30°, respectively, with 30 s of rest between each set. Isokinetic strength testing will consist of 3 sets of 1 maximal effort knee extension and flexion (60/s, concentric/concentric) with 30 s of rest between each set. All testing will be completed on both legs and the largest torque obtained from a given muscle group in any of the strength testing conditions (isometric or isokinetic) will be used to verify leg dominance.

FUNCTIONAL GAIT ASSESSMENT (FGA): The FGA is a valid measure of walking balance and consists of 10 challenging tasks, such as walking with a narrow base of support (i.e., tandem stance), walking backwards, and walking with eyes closed. Each item is graded from 0 (severe impairment) to 3 (normal performance), with a maximum score of 3068. The minimal clinical important difference (MCID) for the FGA has not been established in PwMS. However, in other neurological populations, a MCID of 4-6 points has been suggested.

TIMED 25-FOOT WALK TEST (T25FW): The T25FW test resembles relevant daily life situations, such as walking across a signaled intersection, is well-established and has very good psychometric properties. In a cordoned-off hallway, subjects will be instructed to walk as fast as possible between two points separated by 25 feet during two separate trials65. The shortest time it takes to complete the 25-foot walk will be the main outcome variable. Gait characteristics will also be recorded using six inertial sensors (OPAL inertial motion units [APDM, Portland, OR, USA]) located on the chest/sternum, each wrist and foot, and on the lower back (5th lumbar). A 20% decrease in the time it takes to complete the T25FW has been established as a significant change in PwMS.

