BERG BALANCE SCALE (BBS): The BBS is a valid and reliable assessment of balance during static (e.g., standing with eyes closed) and dynamic (e.g., completing a 360-degree turn) conditions. A cut-off score of 44 has been established as a criterion to identify PwMS with a high fall risk. Furthermore, it has been shown that the minimal clinically important difference (MCID) for the BBS in PwMS is 3 points.

STATIC POSTUROGRAPHY: Static posturography will be examined on a Balance Plate (Balance Tracking Systems, San Diego, CA, USA). Participants will stand on both firm (i.e., the force plate) and compliant (i.e., a 6 cm Airex Balance Pad Elite 76 [Airex AG, Sins, Switzerland] placed on the force plate) surfaces with their eyes open and with their eyes closed for one minute each. The addition of a foam pad increases the difficulty of maintaining balance by changing foot pressure distribution and decreases the input of cutaneous mechanoreceptors and joint receptors. The center of pressure average movement velocity in the anterior-posterior and medial-lateral directions and the area of an ellipse that encapsulates 95% of the 2D area explored will be the primary outcomes.

6-MINUTE WALK TEST (6MWT): The 6MWT is considered the “gold standard” for a long walking test in interventional research. The subjects will be led to a cordoned-off hallway to perform the walk. Subjects will be instructed to walk as far as possible between two points separated by 30 m for 6 min. Gait characteristics and distance walked will be calculated and recorded using six inertial sensors (OPAL inertial motion units [APDM, Portland, OR, USA]) located on the chest/sternum, each wrist and foot, and on the lower back (5th lumbar).

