GAIT TRAINING: The gait training protocol is aimed to improve walking velocity, balance, fatigability, and cognitive functions during motor dual tasks. This protocol has been used previously by Jonsdottir et al. (2018, 2020) and resulted in significant improvements in fatigability, speed, and mobility with a moderate improvement in balance measures. The treadmill training will be performed without body weight support, but subjects may hold onto handrails for balance support if necessary. The exercise intensity will be based on the participant's Rate of Perceived Exertion (RPE) on a scale from 0-10 and the training goal will be to maintain an intensity between 5-6. Therefore, treadmill speed and slope will be regulated based on relative intensity. Heart rate will also be monitored with a heart rate strap placed around the chest. The treadmill training sessions will consist of three different walking bouts: 1) Aerobic bout (minutes 0-12): preferred walking speed for the first 3 minutes, then the treadmill speed and slope will be increased as necessary to maintain the desired RPE range until the end of minute 12. RPE will be maintained between 5-6 and heart rate will not exceed 80% of age-predicted maximum heart rate. 2) Dual-task phase (minutes 13-22): preferred walking speed will be maintained while the participant completes motor dual-task activities such as changing walking motions (e.g., long steps, walking on toes, and knee lifts), head rotations, and walking with eyes closed. 3) Second aerobic phase (minutes 23-34): increase in walking speed and slope as necessary to maintain the desired RPE until the end of minute 31. RPE will be kept between 5-6 and heart rate will remain below 80% of age-predicted maximum heart rate. The last three minutes will consist of walking at their preferred speed.

BALANCE TRAINING: The balance training protocol will be based on previous work by Hebert et al. (2011) and will include a variety of both static and dynamic balance exercises on both compliant (i.e., foam and trampoline) and firm surfaces⁴⁶. Example exercises include performing head rotations and ball catching and tossing during walking and while using a variety of increasingly difficult stances (i.e., heels and toes together, half-tandem, and full tandem stance). Each training session will last approximately 40 minutes.

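### The analysed 6-minute walk distance comes from body-worn sensors with no stated derivation or accuracy, although it can be read directly from the 30 m course.

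*Combined protocol and SAP*

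**What the plan says.** All references are to the combined protocol and SAP.

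- **Course (Section VII.E.6, 6-minute walk test).** "Subjects will be instructed to walk as far as possible between two points separated by 30 m for 6 min". The length of the course is therefore known.
- **Source of the distance (same paragraph).** "Gait characteristics and distance walked will be calculated and recorded using six inertial sensors". The sensors sit on the sternum, lower back, wrists and feet. The paragraph mentions no tally of lengths, floor marks or measuring wheel. It does not say how distance is derived from the signals or how accurate it is.
- **Use in the analysis (Section XI.1).** The stimulation by training by time model, an "ANCOVA with baseline measurements as covariates", "will be conducted on each outcome variable (e.g., distance walked on the 6MWT and FGA score"). Distance on this test is thus an analysed outcome, given as one of two examples.
- **Contrast with the 25-foot walk (Section VII.E.6).** There the shortest time is the main variable and the sensors only add to it: "Gait characteristics will also be recorded using six inertial sensors".
- **What gait training practises (Section VII.E.6).** "The gait training protocol is aimed to improve walking velocity, balance, fatigability, and cognitive functions during motor dual tasks". Its dual-task phase includes "changing walking motions (e.g., long steps, walking on toes, and knee lifts"). The balance training paragraph does not list these.

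**The concern.** An outcome that can be read from the floor is instead estimated from body-worn devices by a method the plan does not describe. If that method adds up estimated strides, two things follow.

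First, it adds random error that a direct reading would avoid. This costs precision in a trial planned on 10 evaluable participants per group. It would also weaken the planned Spearman correlations between change in FDG uptake and change in walking scores, if 6MWT distance is among those scores.

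Second, the error may depend on how a person walks and turns. Section VI.13 selects people who report a difference in function between their legs, and the gait arms rehearse altered step patterns. If walking pattern changes differently between arms, so could the sensor error, and part of an apparent difference in distance could be measurement error rather than distance walked. Such an error could also hide a true difference.

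**Working it through.** **1. The plan's own figure.** Section XI.2 gives Cohen's d = 2.08 and 1.37, significance 0.05, power 80%, and 10 per group (40 in total). I assumed a two-sided, two-sample t-test with SD 1.
- For d = 1.37 and n = 10, the noncentrality is d × √(n/2) = 1.37 × √5 = 3.06 on 18 degrees of freedom. Power is 82.6%, and 10 is the smallest n that reaches 80%.
- For d = 2.08 the same test needs 5 per group.

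The stated 10 per group therefore reproduces from the smaller effect. Section XI.2 does not say which outcome lies behind either d, so using 1.37 for 6MWT distance below is only illustrative.

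**2. Size of a sensor error.** The documents give neither the sensor error nor the expected distance. Both are assumed: error 2-5%, distance 300-500 m.
- Low end: 300 × 0.02 = 6 m.
- High end: 500 × 0.05 = 25 m.
- A 400 m walk is 400/30 = 13.3 lengths, so about 13 turns.

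**3. If the error is purely random.** Let R be reliability, the share of observed variance that is true variance. If 1.37 is the error-free effect, the observed effect is 1.37 × √R. The ratio of error SD to true SD is √((1 − R)/R).

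| R | error SD / true SD | observed d | power at 10 per group | n per group for 80% |
|---|---|---|---|---|
| 1.00 | 0 | 1.37 | 82.6% | 10 |
| 0.95 | 0.23 | 1.34 | 80.6% | 10 |
| 0.90 | 0.33 | 1.30 | 78.5% | 11 |
| 0.80 | 0.50 | 1.23 | 73.6% | 12 |
| 0.70 | 0.65 | 1.15 | 67.9% | 13 |

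The documents give no SD for 6MWT distance, so the 6-25 m range cannot be placed on this table.

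**4. If the error shifts differently between arms.** Suppose there is no true effect, but sensor error alone separates two arms by a given fraction of an SD. The two-sided rejection rate at a nominal 5%, before any Bonferroni adjustment, is:

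| spurious shift (SD) | 10 v 10 | 20 v 20 (main effect) |
|---|---|---|
| 0.1 | 5.5% | 6.1% |
| 0.2 | 7.1% | 9.5% |
| 0.3 | 9.7% | 15.2% |
| 0.5 | 18.5% | 33.8% |

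The shift here is a difference between arms. The 6-25 m in step 2 is an error per test and must not be read as that difference.

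**5. What baseline adjustment does.** A sensor offset that stays the same within a person is present at baseline and at follow-up, so the baseline covariate largely absorbs it. A change in error that is equal in all arms cancels in the contrast. Only a change in error that differs between arms biases the comparison.

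**The case against.** **The mechanism is inferred.** A reader might conclude that the endpoint does carry a gait-dependent error. The documents do not support that. They name no algorithm, and the sensors are not on the feet alone. A method that detects turns and multiplies lengths by 30 m fits the text equally well, and its error would not depend on stride in this way. This stands, and it is why the point is conditional. It does not settle the matter for the plan: the method is still unstated, and a part-length at 6 minutes must still be obtained.

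**The route to bias is narrow.** Bias needs an error that changes differently between arms. The first hypothesis in Section I.5 compares tDCS with sham, and both training types appear on each side. This stands for that contrast, although the same section also expects the largest gains in the gait-plus-tDCS group, which brings in training type.

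**Counting is not exact.** A missed length costs 30 m, more than the top of the assumed 6-25 m range. A sensor reading also needs no observer, which has value in a trial described as double-blind. This stands, and it is the reason to keep the sensors as a check.

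**The outcome is not called primary.** Section XI.1 names "distance walked on the 6MWT and FGA score" only as examples, and the 6MWT paragraph claims no primary status. The timed 25-foot walk already gives a directly measured walking outcome. This limits the weight of the point.

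**Conclusion.** The point holds in a limited form. The plan takes an analysed distance from an undescribed indirect method on a course where a direct reading is available. It already keeps the two roles apart for the 25-foot walk.

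The harm is possible rather than shown. It depends on the distance being built from strides, and bias further depends on the error changing differently between arms. Under assumed values the effect runs from negligible (R = 0.95, power 80.6%; a 0.1 SD shift, error rate 5.5-6.1%) to material (R = 0.70, power 67.9%; a 0.5 SD shift, error rate 18.5-33.8%). Nothing in the documents says where in that range the trial would fall.

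A reader might also infer that the sample size is undermined. It is not: 40 evaluable and 48 recruited stand as far as this point goes. The case for acting is that the change costs very little and helps whichever way the sensors work. A direct distance not recorded on the day may not be recoverable.

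**What to change.** In the 6-minute walk paragraph of Section VII.E.6:

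- Define the analysed distance as completed 30 m lengths × 30, plus the measured part-length at 6 minutes.
- Have the staff member present record it on a tally sheet at Sessions 2, 12, 13 and 14.
- Keep the inertial sensors for gait characteristics and as a cross-check on the number of lengths. State how the sensor distance is derived, and how a disagreement is resolved without reference to group.

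The cost is a short text change, a tally sheet, and a tape or floor marks. Section VIII.2 already places staff close to each participant, so no visit, person or device is added. The one downside is a miscounted length, a 30 m error that the sensor check should catch.
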